	UACR (x3)		x	x	x	x	DS	DS	DS
	Biomarkers		x	x		DS	DS		
Group	Immediate Start		x	x	x				
	Delayed Start		x	x	x	x	x	x	x

*CBC, Renal Panel, Ferritin, TSAT

** V1 if consent: CBC & eGFR panel

DS = Delayed Start ONLY

This is a two-arm, open-label, single-center, randomized controlled trial to understand the mechanisms of EIH. Participants will be randomized based on stratum of baseline level of urine albumin/urine creatinine ratios (UACR) measured on three consecutive days. The primary analysis will compare the 80 participants in the early start group to the 80 in the delayed start (DS) or waitlisted group over the first 12 weeks. All procedures will be performed as listed in the table based on study visit. Confirmatory analysis will compare the first 12 weeks to the next 12 weeks in the DS group. Accordingly, the study procedures labeled DS will be performed only in the delayed start randomized participants.

Study Intervention

Participants with CKD and anemia who meet the inclusion and exclusion criteria will be randomized to either the immediate or delayed start group. There are at least 7 study related visits in the early start group, and 11 in the waitlist group. Two consecutive days are needed to perform 24h ambulatory BP monitoring, which will be done twice in the immediate start group and 3 times in the delayed start group. Patients will receive oral iron (ferrous sulfate, 324 mg orally twice daily) if serum ferritin concentration is <100 ng/mL or transferrin saturation is <20%. If clinic BP exceeds either 179 mmHg systolic or 109 mmHg diastolic or if clinic BP raises by >20/10 mmHg compared to baseline, antihypertensive medication dose will be increased or a new antihypertensive will be added.

Participants will be identified in the renal clinic or the electronic medical record system based on estimated GFR and Hgb. At baseline, all participants will have 24-h urine Na measured to assess dietary Na intake.

Treatment Adherence

We recognize the limitations of syringe count, but we will assess treatment compliance with the study drug by performing a syringe count at each of the study visits.

Protocol for the management of anemia

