Harms will be assessed by monitoring changes in weight, eGFR, CBC, clinic BP, and ABPM. For more definitive assessments, including hospitalizations, serious adverse events will be properly completed and sent to the VAMC DMC as requested. Safety of continued participation will be assessed at each study visit. The stop-points will be treatment-emergent severe adverse events that precludes further exposure to the drug, such as an allergic drug reaction, initiation of renal replacement therapy, or death. If the study drug is stopped, the subject will be continued to be studied so as to not violate the intention-to-treat principle.

Participants

Inclusion Criteria

- Stage 3 or 4 CKD defined as eGFR <60mL/min/1.73m² for ≥3 months or persistent albuminuria for ≥3 months; (i) urine albumin to creatinine ratio of more than 30 mg/g; (ii) urine protein to creatinine ratio of more than 150 mg/g; or (iii) at least 1+ dipstick positive proteinuria. ⁸⁸
- 24h ABPM <140/90 mmHg at baseline in the presence or absence of antihypertensive treatment.
- Hgb between 8 and 10 g/dL.
- No treatment with ESA within the previous 3 months.
- Adults, age 18 and older.

Exclusion Criteria

- Need for packed RBC transfusion in the previous 2 months.
- Myocardial infarction, stroke, or hospitalization for heart failure in the past 2 months.
- In the assessment of the investigator, have hematologic, inflammatory, infectious, or other conditions that might interfere with the erythropoietic response.

Retention of Participants

For half of the participants, only 7 visits are needed. For the others, at least 11 visits over 24 weeks of the trial are needed. We will offer \$20 per visit for participation in the trial to offset travel and time costs.

METHODS

Method of Randomization

Participants will be randomized in a 1:1 ratio to either early or delayed treatment (“waitlisted group”) with EPO according to UACR strata. A random permuted block design will be used to avoid imbalance in assignment to the treatment groups over time. A randomization sequence will be generated by the statistician and individually concealed in sequentially numbered opaque envelopes. After confirming eligibility with the principal investigator, the study pharmacist will dispense EPO according to the randomization sequence.

Measurement of clinic BP

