The number of subjects who experience hypokalemia, hypercalcemia, gout, hospitalization for diabetes mellitus, transient elevations in serum creatinine concentration, and symptomatic orthostatic hypotension will be counted for each group and compared using a Poisson regression model using terms for treatment and treatment x stratum. The statistical significance of the treatment term will be used to indicate differences between CTD and placebo. If the interaction term is significant then the event rates will be reported for each stratum. The mean change from baseline in serum potassium, calcium, estimated GFR, uric acid, HgbA1C, PTH intact, and orthostatic BP will be calculated using mixed models as noted above.

Alternative study design considerations and clarifications

Choice of non-dialysis patients. Dialysis patients are challenging to study because it is more difficult to determine hypertension due to confounding by dry weight. Angioaccess makes it difficult to perform FMD. Furthermore, the number of dialysis patients—in contrast to CKD patients not on dialysis—is limited.

Timetable/Milestones

We expect to recruit and randomize a total of 160 participants in the first 3.5 years and complete the study in 4 years. This will require approximately 1 participant to be randomized per week. See table below.

Table 1: Timeline for randomization in the trial (t = 4y, n = 160)

	Year 1				Year 2				Year 3				Year 4			
Quarter	1	2	3	4	1	2	3	4	1	2	3	4	1	2	3	4
Patients	x	16	16	16	16	12	12	12	12	10	10	10	10	8	x	x

Feasibility

A feasibility assessment was performed using data from the Veterans Administration's Corporate Data Warehouse (CDW), a national repository of data compiled from the electronic medical record (EMR) system used by the Veterans Health Administration (VHA). These data include current and historical values from multiple domains such as patient medications, vitals, labs, procedures, and diagnoses, and are available from October 1st, 1999 forward. Of note, these data are updated on a daily basis and are neither filtered nor validated prior to entry into the CDW. We will use these values to screen potentially eligible participants. It is only possible to uniquely identify potential participants by accessing their EMRs using real social security numbers.

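### The only kidney event in the between-group safety count is a transient creatinine rise, so a rise that persists or ends in dialysis is not counted

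*Combined protocol and SAP*

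**What the plan says.** The Safety analysis section (under Statistical Methods) lists six event types to be counted by group and compared with a Poisson regression. The kidney item appears in "transient elevations in serum creatinine concentration, and symptomatic orthostatic hypotension will be counted for each group". It has no size threshold, no rule for what counts as recovery and no time window. The next sentence says the treatment term will indicate differences between CTD and placebo. The section then adds mixed models for "The mean change from baseline in serum potassium, calcium, estimated GFR, uric acid, HgbA1C, PTH intact, and orthostatic BP", which is the only other kidney measure in the safety analysis.

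Safety Assessments and Variables states that "Harms will be assessed by monitoring changes in weight, eGFR, CBC, clinic BP, and ABPM". It gives as stop points severe treatment-emergent events "such as an allergic drug reaction, initiation of renal replacement therapy, or death", and says that "serious adverse events will be properly completed and sent to the VAMC DMC as requested". Patients who stop study drug stay in follow-up. No between-group analysis of serious adverse events is specified.

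In Figure 2, blood labs ("CBC, Renal Panel, Ferritin, TSAT") are drawn at baseline and weeks 4, 8 and 12 in both arms. The week 16, 20 and 24 draws are marked DS, and "the study procedures labeled DS will be performed only in the delayed start randomized participants".

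**The concern.** The adjective transient turns the usual ordering of severity around. The milder course, a rise and a recovery, scores as an event. The worse course, a rise that stays up or leads to dialysis, does not. The participants all have CKD, and the trial's hypothesis is that the drug raises blood pressure, so sustained loss of kidney function is a harm readers will look for. A comparison restricted to recovered rises can understate a real excess on EPO, or reverse its direction if more of the EPO rises persist.

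A second difficulty follows from the same word. Calling a rise transient requires a later, lower value, and the plan does not say how late that value may be taken. After week 12 only one arm has scheduled panels.

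**Working it through.** The plan states no figure for kidney events, so there is none to reproduce. The check has four steps. Steps 2 to 4 use assumed rates, labelled as such.

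**1. What each kidney outcome feeds into (from the documents)**

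| Outcome | Between-group event count | Elsewhere in the plan |
|---|---|---|
| Creatinine rises, then recovers | Yes | Mean eGFR change |
| Creatinine rises and stays up | No, read literally | Mean eGFR change |
| Renal replacement therapy starts | No | Stop point; serious adverse event reporting |

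**2. Effect of counting only recovered rises (assumed shares)**

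Apparent EPO/control ratio = true ratio for any rise × (1 − persistent share on EPO) / (1 − persistent share on control). Assume a true ratio of 2.0 and 25% of control rises persistent.

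- 50% of EPO rises persistent: 2.0 × 0.50 / 0.75 = 1.33.
- 75% of EPO rises persistent: 2.0 × 0.25 / 0.75 = 0.67.

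A true doubling appears as a 33% excess in the first case and as a deficit in the second.

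**3. Can the mean eGFR change stand in for the missing event? (assumed rates)**

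Assume 10% of EPO and 5% of control patients lose 30% of eGFR and the rest do not change. In 80 per arm that is 8 v 4 patients, and the event count is 0 v 0.

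- Mean difference = 0.05 × 0.30 × baseline eGFR. Baseline 30 gives 0.45; baseline 45 gives 0.68 mL/min/1.73 m².
- Standard error = SD of change × √(2/68), using the plan's 68 completers per arm. SD 5 gives 0.86; SD 8 gives 1.37.
- Two-sided 5% power (normal approximation): 6.2% (baseline 30, SD 8) to 12.3% (baseline 45, SD 5).

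For comparison, an event count of 10% v 5% has about 20% power with 68 per arm. That is better but still low.

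**4. Is there a later scheduled renal panel on which to judge recovery?**

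The renal panel is taken to include creatinine.

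| Rise first seen | Immediate start | Delayed start, all visits | Delayed start, weeks 0-12 only |
|---|---|---|---|
| Week 4 | Yes | Yes | Yes |
| Week 8 | Yes | Yes | Yes |
| Week 12 | No | Yes (week 16, on EPO) | No |

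If the week-16 sample is used for rises with onset by week 12, three draws can be classified in the delayed start arm and two in the immediate start arm. Assume one-visit rises with probability p at each visit and no true difference. The expected ratio is [1 − (1 − p)²] / [1 − (1 − p)³].

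- p = 0.03: 0.68.
- p = 0.05: 0.0975 / 0.1426 = 0.68, or 7.8 v 11.4 of 80 patients.
- p = 0.10: 0.70.

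If only weeks 0-12 are used, both arms have two classifiable draws and the ratio is 1.0. Week-12 rises can then be classified in neither arm.

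**The case against.** The strongest reply is that the paragraph was probably not written for this study. It compares CTD with placebo, but the trial is open label with neither arm, and the documents tie several of the listed events (gout, hypercalcemia, hypokalemia) to nothing in the EPO rationale. On this view transient was never a considered kidney endpoint, and repairing one of six items misses the larger problem. The diagnosis is fair, and the whole list should be checked. It does not remove the point: this is the only event analysis for safety in the plan, and correcting the arm labels alone would leave the kidney item as it is.

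It can also be said that sustained harm is not invisible. This is correct. eGFR is monitored and modelled, renal replacement therapy is a named stop point, serious adverse events go to the DMC, albuminuria is measured every 4 weeks, and a data and safety monitoring plan exists that is not reproduced here. What is missing is a between-group count. A persistent rise without hospitalization need not be reported as a serious adverse event.

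Two stronger readings are tempting and are not supported.

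- A reader might infer that the schedule necessarily biases the count against the control arm. The section sets no window, and the trial design section defines the parallel-group comparison over the first 12 weeks, where this bias is zero. It arises only if recovery is judged on samples that one arm alone provides. The immediate start arm is also described as having at least 7 visits, so an extra panel is possible, though none is scheduled.
- A reader might compare all follow-up and quote an apparent ratio of 0.42-0.46 (two classifiable draws v five, p = 0.03-0.10). Most of that departure comes from unequal follow-up. Counting any rise over 3 v 6 visits, with no recovery requirement, already gives 0.52-0.58.

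**Conclusion.** Wrong as written. That the single kidney event counts recovered rises and omits persistent ones and dialysis follows from the text and needs no assumption. Its numerical effect cannot be taken from the documents. Under the assumed 10% v 5% with a lasting 30% loss, the count shows 0 v 0 and the mean eGFR change would detect the difference about 6-12% of the time.

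The week-12 problem is conditional. It exists if the week-16 sample is used, and under a strict 0-12 week window it becomes an inability to classify any week-12 rise in either arm. It should not be reported as an established bias.

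The primary blood pressure analysis is unaffected. The consequence is confined to what the trial can say about kidney safety.

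**What to change.** In the Safety analysis section, replace the creatinine item with: a rise in serum creatinine of at least a fixed percentage over baseline (threshold set in advance by the sponsor, for example 30%) at any renal panel after baseline through week 12, or initiation of renal replacement therapy from randomization through week 12. Count it identically in both arms whether or not it recovers. Both components need the same window; otherwise delayed start patients could be counted for dialysis up to week 24.

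Report recovery status (recovered, persistent, unknown) descriptively, and do not use creatinine values after dialysis start to declare recovery. If eGFR after dialysis start is handled specially in the mean change, state a rule that keeps these worst outcomes in, for example a sensitivity analysis assigning a low eGFR value. Simply dropping them could favour the arm with more dialysis.

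In the same revision, correct the reference to CTD and placebo and check every listed event and laboratory mean against this study.

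The cost is a few sentences and no new samples, since the panels are already drawn every 4 weeks. There are two downsides. More patients will be counted as having a kidney event, and power stays low (about 20% for an assumed 10% v 5%), so the result should be given as an estimate with a confidence interval, and a non-significant difference should not be read as evidence of safety.

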On the other hand, HIF stabilizers may raise EPO to more physiologic levels, reduce crosstalk with vascular EPO-receptors, and mitigate hypertension. A 2014 study demonstrated in a rodent model that compared to EPO, treatment with HIF-stabilizer molidustat corrected anemia associated with subtotal nephrectomy. However, in contrast to EPO, molidustat reduced systolic BP in a dose-dependent manner⁸². The authors postulate that anti-inflammatory and anti-fibrotic effects of the drug on the kidney may be operative. This study further illustrates that increment in Hgb can be dissociated from an increment in BP. Human data are available but are thus far inadequate to address the question of risk for or protection from incident hypertension with HIF stabilizers ⁸³⁻⁸⁶.

RESEARCH PROTOCOL AND TRIAL DESIGN

Overall trial design and plan

To test the notion that EPO treatment in anemic patients with CKD and stage 1 or less hypertension that is treated or untreated with antihypertensive medications will raise BP, we propose a randomized controlled trial with a “waiting-list design” as shown in **Figure 2**. In this design, half of the patients are treated immediately with EPO and the other half are put on a waiting list for 12 weeks, after which they begin treatment. Ultimately, the waitlisted patients are exposed to the intervention, thus serving as their own controls. The design allows between-group comparison by comparing responses in the parallel groups over 12 weeks and within-group comparison for the waitlist group in the second 12 weeks compared to the first 12 weeks. Titration of the dose of EPO will occur every 4 weeks to manage anemia as detailed below. The effect of EPO on BP will be assessed by change in diastolic ambulatory BP measured over 24 hours at baseline and again at 12 weeks in both groups and at 24 weeks in the waitlisted group. At baseline and every 4 weeks thereafter, we will also evaluate changes in clinic BP and albuminuria. At baseline and 4 weeks after intervention, we will measure endothelial function, and collect blood for biomarkers. The biomarkers we will be analyzing are renin, aldo, ET-1, catecholamine, ADMA, and urine nitrates and nitrites.

Figure 2: Trial design and study process

Visit		1	2-3	4	5	6-7	8	9	10
Measurement		Consent	Baseline	Week 4	Week 8	Week 12	Week 16	Week 20	Week 24
PROC	FMD		x	x		DS	DS		
HTN	24h-ABPM		x			x			DS
	Clinic BP	x	x	x	x	x	DS	DS	DS
Labs	24h-urine		x			x			DS
	Blood labs*	x**	x	x	x	x	DS	DS	DS

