Darbepoetin will be self-administered subcutaneously at a starting dose of 0.45 µg/kg once weekly. Hgb will be targeted between 10-12 g/dL with a goal of at least 2 g/dL increment from baseline. If a patient's Hgb increases by 2 or more g/dL during any 4-week period, the darbepoetin dose will be decreased by 25%. If Hgb rise over 4 weeks is < 1g/dL and patient is not in target Hgb range the dose of darbepoetin may be increased by 25%. If Hgb change from baseline is between 1 - 2 g/dL the dose of darbepoetin will be maintained. If Hgb concentration increases to >12.0 g/dL, the drug will be withheld until Hgb concentration falls to <12 g/dL, at which time it may be restarted at a dose 25% lower than the previous dose.

In a Phase III registration trial of darbepoetin in CKD,⁸⁷ the median response time to increase in Hgb was 7 weeks. The response was defined as an increase in Hgb of ≥ 1 g/dL from baseline and Hgb ≥ 11 g/dL. The peak response was achieved at 13 weeks. Since we want to magnify the difference between groups, a 12-week treatment period appears appropriate. We expect about half of the participants to be treated for 24 weeks since the waitlisted group will be treated after 12 weeks.

Stop points

1. Stop point for severe anemia: If Hgb drops to <8 g/dL, waitlisted patients (delayed start group) will be started on EPO therapy without further delay. In the TREAT trial, where the rescue threshold was 9 g/dL, less than half (46%) of the patients in the placebo group needed at least one dose of EPO over the life of the trial ¹⁰. The target for rescue therapy is even lower in this trial and we do not expect many patients to be taken off the waitlist.

2. Stop point for uncontrolled hypertension: If clinic BP exceeds either 179 mmHg systolic or 109 mmHg diastolic, or rises by >20 mmHg/10 mmHg, antihypertensive medication dose will be increased, or a new medication added.

Safety Assessments and Variables

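### The safety comparison sets no time window or exposure term for arms followed 12 and 24 weeks, so if all follow-up is counted, real harm could appear as protection

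*Combined protocol and SAP*

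**What the plan says.** **Safety model (Safety analysis).** Subjects with each listed event "will be counted for each group and compared using a Poisson regression model using terms for treatment and treatment x stratum". The section adds: "If the interaction term is significant then the event rates will be reported for each stratum". It defines no denominator for those rates. It describes the test this way: "The statistical significance of the treatment term will be used to indicate differences between CTD and placebo".

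**Design.** On allocation (Method of Randomization): "Participants will be randomized in a 1:1 ratio to either early or delayed treatment". On timing (Overall trial design and plan): "half of the patients are treated immediately with EPO and the other half are put on a waiting list for 12 weeks". The Hypothesis section gives the delayed arm a further 12 weeks on EPO after the wait.

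**Follow-up.** Under Retention of Participants, half of the participants need only 7 visits. "For the others, at least 11 visits over 24 weeks of the trial are needed". In the Figure 2 schedule, every assessment after week 12 is marked as delayed start only. Safety Assessments and Variables calls for a safety check at every study visit.

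**Exposure (Protocol for the management of anemia).** "We expect about half of the participants to be treated for 24 weeks since the waitlisted group will be treated after 12 weeks". Under Stop points, a waitlisted patient whose Hgb falls below 8 g/dL starts EPO early.

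**The concern.** The two arms are observed for different lengths of time by design, and the longer observation in the delayed arm includes EPO treatment. A count of affected subjects per arm, compared without a window or an exposure term, mixes the drug effect with the length of follow-up. The delayed arm has 12 more weeks in which to record an event, and those weeks are on drug. The control arm then carries both its own background events and a full course of on-drug events.

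At stake is the only planned between-group test of the listed adverse events. Two analysts who follow the section in good faith could report ratios on opposite sides of 1 from the same data. The contrast named in the section belongs to neither arm, so the label does not settle what is being compared.

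**Working it through.** **The plan's own figure.** The section gives no numbers for safety, so the denominator is the randomised number per arm. Sample Size uses an SD of the difference of 10.3 mmHg, a difference of 5 mmHg, two-sided tests and 80% power. Alpha is not stated; I assume 0.05. The normal approximation gives n = 2 × (1.960 + 0.842)² × 10.3² / 5² = 66.6, so 67. The two-sample t calculation gives 67.6, so 68 per group, as stated. Then 68/0.85 = 80 per group. The figure reproduces.

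**Inputs for the safety check.**
- From the documents: 80 per arm; immediate arm 12 weeks on EPO; delayed arm 12 weeks waiting and then 12 weeks on EPO (Hypothesis; Overall trial design and plan).
- Assumed, because the documents give no event rates: off-EPO risk p per 12 weeks of 5%, 10% or 20%; rate ratio RR on EPO; constant rates; no dropout.

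**Events, all follow-up counted.** Let L = −ln(1 − p) be the 12-week off-EPO hazard.
- Immediate arm: 80 × L × RR over 960 person-weeks.
- Delayed arm: 80 × L × (1 + RR) over 1,920 person-weeks.
- Ratio = RR/(1 + RR), which is below 1 for every RR: 0.50 at RR 1, 0.60 at 1.5, 0.67 at 2, 0.75 at 3, 0.83 at 5.

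**Affected subjects, which is what the section counts.** Immediate: 80 × (1 − e^(−L·RR)). Delayed over 24 weeks: 80 × (1 − e^(−L·(1+RR))). Delayed over weeks 0-12: 80 × p. At p = 10%:

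| True RR | Immediate | Delayed, 24 weeks | Ratio | Delayed, weeks 0-12 | Ratio |
|---|---|---|---|---|---|
| 1 | 8.0 | 15.2 | 0.53 | 8.0 | 1.00 |
| 2 | 15.2 | 21.7 | 0.70 | 8.0 | 1.90 |
| 3 | 21.7 | 27.5 | 0.79 | 8.0 | 2.71 |

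At RR 2 the all-follow-up ratio is 0.68 at 5% risk and 0.74 at 20%.

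**How often a test would mislead.** I used 200,000 simulated trials per setting, with a Wald test on the log ratio of subject counts and SE = √(1/a + 1/b). For RR 1.5, 2 and 3 in turn, with all follow-up counted:

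| Off-EPO risk | Fewer affected in immediate arm | Significantly protective |
|---|---|---|
| 5% | 81%, 78%, 73% | 11%, 10%, 7% |
| 10% | 90%, 87%, 82% | 20%, 14%, 8% |
| 20% | 97%, 94%, 89% | 28%, 17%, 5% |

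A significantly harmful result appears in under 0.2% of trials in every one of these settings. At RR 2, the significantly protective share falls to about 2% at a 2% risk and 0.1% at a 1% risk.

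**Would a follow-up offset be enough?** With each arm's full person-time, the rate ratio is (80·L·RR/960) / (80·L·(1 + RR)/1,920) = 2RR/(1 + RR). That gives 1.20, 1.33 and 1.50 for true RR 1.5, 2 and 3. The inversion goes, but harm is diluted because half of the delayed arm's time is on EPO.

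**Dropout.** If 15% of the delayed arm alone left at week 12 (an assumption), the event ratio is RR/(1 + 0.85·RR). This stays below 1 for RR under 1/0.15 = 6.7.

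**Planned exposure under the two readings.** Twelve weeks on EPO in each arm: 80 × 12 + 80 × 12 = 1,920 patient-weeks. Twenty-four weeks on EPO for half: 80 × 12 + 80 × 24 = 2,880.

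**The case against.** The strongest reply is that a 12-week window is already implied. Overall trial design and plan describes the between-group comparison as one over 12 weeks, and keeps the second 12 weeks for comparison within the waitlist arm. On that reading there is no inversion: RR 2 at 10% risk gives 1.90. This has weight, and it makes the inversion conditional. But that passage says what the design allows; it does not define the safety count. The window in the paragraph after Figure 2 is for the primary analysis. Where the authors intended a window for an event-type outcome they wrote one: hypertension status is compared between groups over the first 12 weeks by logistic regression, and weeks 12-24 go to a within-group McNemar test. The safety section has no equivalent, and its mention of event rates supplies no denominator.

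A reader might also infer that the trial's central adverse effect, hypertension, is affected. It is not: it is absent from the safety event list, and it has its own windowed analysis. Nor do the documents tie events such as gout or low potassium to EPO, so the RR values above are illustrative.

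A reader might infer as well that safety monitoring would be misled by the 24-week exposure statement. The documents do not show that. The sentence sits in a rationale paragraph, safety is reviewed at each visit, serious events go to the DMC, and the monitoring plan itself is not in view.

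**Conclusion.** The point holds in conditional form. As written, the safety comparison has no window, offset or on/off-EPO term, across arms with 12 and 24 weeks of follow-up, and it names a contrast between arms that do not exist in this trial. If all follow-up is counted, the event ratio is RR/(1 + RR), so the estimate falls below 1 whatever the true effect. At an assumed 10% risk, a doubling of the rate shows as 0.70 instead of 1.90.

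It would go too far to say that a harmful drug will look protective. That requires weeks 12-24 of the delayed arm to enter the counts, which the section neither states nor excludes. Nor would false protection usually be significant. With true harm it is significant in about 5-28% of trials across 5-20% risk and RR 1.5-3, and less often for rarer events. A share near 46% arises only for a drug with no effect at an assumed 20% risk, so it says nothing about a harmful drug. The damage is mainly to the point estimate, and to the near-absence of any chance of detecting harm.

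These sizes rest on constant rates, 80 per arm, full follow-up and assumed risks. The primary endpoint and sample size are not affected.

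**What to change.** Rewrite the Safety analysis section as follows.

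1. Name the contrast as immediate start against delayed start.
2. Restrict the randomised comparison to events with onset from randomisation to week 12. Analyse either subjects with an event in that window, or events with log person-time in that window as the offset. An offset over all follow-up is not a substitute, since a true RR of 2 would appear as 1.33.
3. Report weeks 12-24 of the delayed arm separately, within group, as on-EPO events.
4. Flag waitlisted participants who start EPO early under the rescue rule during weeks 0-12, so that on-drug time in the control arm is visible.
5. Reconcile the 24-week treatment statement in the anemia-management section with the Hypothesis and Overall trial design sections, so that planned exposure is stated once and consistently (1,920 or 2,880 patient-weeks under the two readings).

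The cost is wording in the protocol and SAP; no visit or measurement changes. The downside is that events in weeks 12-24 leave the between-arm test. The windowed test also has limited power for uncommon events: at RR 2 it reaches significance in about 12%, 29% and 46% of simulated trials at 5%, 10% and 20% risk. Estimates should therefore be shown with confidence intervals.
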